9.2.2 Reporting SUSARs

The Sponsor (HUTH R&D dept.) will report fatal or life-threatening SUSARs to the MHRA within 7 days and follow-up information within a further 8 days. The sponsor will send all other SUSAR reports to the MHRA within a maximum of 15 days. The Sponsor will report fatal or life-threatening SUSARs to the Research Ethics Committee (REC) within 7 days and follow-up information within a further 8 days by following the request on the Serious Event Initial and Follow-up report forms. The Sponsor will send all other SUSAR reports to the REC within a maximum of 15 days.

9.2.3 Expected Serious Adverse Events

Due to the seriousness of the disease in this study, the following expected SAEs will not require reporting within 24hrs on the initial and follow-up SAE forms, but will still need to be reported on the trial AE report form.

Expected serious adverse events in this trial include:

Expected Serious Adverse Events

Hospital admission due to respiratory condition

Admission to hospital or prolongation of existing hospitalisation for a pre-existing condition such as heart failure

Death due to exacerbation of respiratory disease or known pre-existing condition

Elective surgery

Hospital admissions and deaths are common in certain patient groups in the study, such as COPD and ILD, due to their underlying disease. Thus, admissions related to such participants' underlying condition or co-morbidities will be classified as an expected SAE in which case the report will not have to be submitted within the timeframe of 24 hours but should be recorded in the participant's CRF.

9.3 Pregnancy Reporting

If a trial participant becomes pregnant whilst participating in the trial, the patient will be withdrawn from trial treatment but will continue to be followed-up for trial outcomes. The pregnancy will not be considered an AE. The patient will be followed up by one to two monthly visits/telephone contacts during pregnancy, and at birth and at 3 months after the birth of the baby. Should there be a congenital anomaly or birth defect, then this will be reported as an SAE/SAR/SUSAR.

9.4 Reporting urgent safety measures

If any urgent safety measures are taken the Sponsor shall immediately and in any event no later than 3 days from the date the measures are taken, give written notice to the MHRA and the relevant REC of the measures taken and the circumstances giving rise to those measures. These urgent safety measures may be taken without prior authorization from the MHRA, EC or Trust (HUTH R&D). The investigator must alert HUTH R&D (Sponsor) as soon as possible of the urgent measures taken by contacting the R&D Office telephone number [name] or [name] (Mon - Fri 8am – 5pm) or the Trust Switchboard [name] (out-of-office hours) and asking for either the R&D Manager ([name]) or R&D Director ([name]). The CI/PI or HUTH R&D should phone the Clinical Trial Unit at the MHRA and discuss the issue with a medical assessor as soon as possible. Contact the MHRA CTU via the clinical trials for medicines helpline [name] (Monday - Friday 08.30am to 4.30pm).HUTH R&D should notify pharmacy clinical trials staff as soon as possible. The CI/PI must notify the MHRA, REC and Trust (HUTH R&D) in writing within 3 days after the urgent measures have been taken, by emailing the clinical trial helpline at [contact] and by submitting a substantial amendment notification form. Note that if the decision is made with HUTH R&D to halt the study due to the urgent safety measures then this can be added to the substantial amendment form and would save submitting another substantial amendment for the temporary halt.

The substantial amendment form and any supporting documents should be sent with a covering letter detailing;

- the urgent measures taken
- > the reasons for them
- the medical assessor contacted

9.5 Development safety update reports

The PI will provide (in addition to the expedited reporting above) DSURs once a year throughout the clinical trial, or on request, to the Competent Authority (MHRA in the UK), Ethics Committee and Sponsor. The MHRA approved SmPCs will need to be reviewed for up-dates annually at the time the DSUR is completed. If the SmPC(s) has been updated, the PI and Sponsor will risk assess the changes and decide if they have an impact on patient safety. If the decision is that the updated SmPC(s) need to be used as the new Reference Safety Information (RSI) then this must be submitted to the MHRA as a substantial amendment. The updated SmPC(s) can be used once approved by the MHRA. The report will be submitted within 60 days of the Developmental International Birth Date (DIBD) or the MHRA clinical trial authorisation of the trial each year until the trial is declared ended.

9.6 Concerns with the Investigational Medicinal Product

The investigator team must alert the Sponsor straight away of any concerns regarding the IMP, this may be to do with the expiry of the IMP or the reaction of patients to the IMP or other concerns. The Sponsor will inform pharmacy and with pharmacy and the PI will decide whether it is appropriate to trigger the IMP recall SOP.

9.7 Notification of serious breaches to GCP and/or the Clinical Trial Protocol

A serious breach is defined as likely to effect to a significant degree:

- (a) the safety, physical or mental integrity of the patients
- (b) the scientific value of the trial

The Sponsor will be notified immediately of any case where the above definition applies during the trial conduct phase.

The Sponsor will notify the competent authority in writing of any serious breach of:

- (a) the conditions and principles of GCP in connection with this trial
- (b) the Clinical Trial Protocol and its amendments (if applicable) relating to this trial within 7 days of becoming aware of that breach.

Safety Assessments:

The collection and reporting of data on adverse events and serious adverse events will be in accordance with ICH GCP and The UK framework for health and social care research.

10. DATA HANDLING AND QUALITY ASSURANCE

10.1 Data Collection

Investigators will enter the information required by the protocol onto the CRFs in accordance with the CRF Completion Instructions that are provided with the CRFs. Source Data Verification will be performed by the HUTH R&D Clinical Trials Monitor at regular intervals during the study according to the Monitoring Plan. Data discrepancies will be flagged to the investigator and any data changes will be recorded in order to maintain a complete audit trail (reason for change, date change made, who made change).

10.2 Database, Data Handling, and Quality Assurance

All data management (use, control, storage) will be according to the requirements of the General Data Protection Regulation 2018. The database will be password protected and stored on a shared drive belonging to the Hull University Teaching Hospitals NHS Trust. Access will only be granted to staff associated with the trial that already agree and abide to the HUTH CP134 – Confidentiality and Information Security Policy. These staff will have individual log in and password details. Entry of data to database will be via transfer of information from paper copy (Case Report Form) with all information necessary as delineated by protocol

Participants will be informed that their personal data will be pseudo-anonymised and related forms and questionnaires will be identified using a participant trial number only. All hard copy data will be stored in a locked filing cabinet in accordance with data protection requirements for the retention of research data and local site data management policies.

The main trial database will be developed by the Respiratory Clinical Trials Unit at Castle Hill Hospital. Access to the database is controlled by encrypted password on secure NHS computers

at the Respiratory Clinical Trials Unit. The Sponsor will review the database prior to data entry and ensure there is an audit trail *in-situ*.

HUTH IT Services Department has a backup procedure approved by auditors for disaster recovery of files held on the Y: drive servers. The servers are backed up to disk media each night. The disks run on a 4 week cycle. Files stay on the server unless deleted by accident or deliberately. Anything deleted more than 4 weeks previously is therefore lost. Additional 'archive' backups are taken for archived data, so data should not be lost from this type of system. Disks are stored in a fireproof safe.

Direct access will be granted to authorised representatives from the Sponsor, host institution and the regulatory authorities to permit trial-related monitoring, audits and inspections- in line with participant consent.

Trial documents (paper and electronic) will be retained in a secure location during and after the trial has finished.

10.3 Hyfe Cough Tracker© Cough Data Storage

All participants are provided a unique study ID and will also be provided with a unique Hyfe Cough Tracker app user identifier if they provide consent to participate in this activity. Only local investigators will have access to the key allowing for linkage of cough data and recordings with patient identification and any other metadata collected as part of the study.

Putative cough sounds (i.e., "explosive" sounds) recorded using the Hyfe Research app will be <0.5 seconds in duration and uploaded to a secure server. Non-explosive sounds are immediately discarded upon processing. The short length of the recordings means they cannot be used to identify the patient (unlike prolonged sound recordings, like Amazon's Alexa device). Standard data encryption and safety tools will be employed.

At all points, participants can opt out of the study and monitors/phone apps will be removed. Our consent process will explicitly describe exactly what is and is not recorded. We will employ standard data encryption and safety tools at rest and in transit. Specifically, this project will use the Hyfe Cough Tracker app, which uses the Google Cloud platform for data management and storage. Firebase uses industry-standard encryption and security protocols.

Fire store, the Google Cloud storage architecture (where audio files and associated meta-data are stored) is HIPAA-compliant. Both audio files and associated meta-data are encrypted in transit using HTTPS. When the server receives a file, it is processed through the Hyfe algorithms, and sounds likely to be cough are stored in <=0.5 second files on encrypted disks.

Data will be transferred from Hyfe to the research team via a data dump occurring at regular intervals (usually one week). Each research participant/site will be associated with a "Hyfe ID" number; all audio files and meta-data transferred from Hyfe to the research team will be linkable to the study participant/site via this "Hyfe ID" number. Hyfe will not have access to the study participants' identity. Basic non-identifiable demographic information such as year of birth, sex, and diagnosis will be shared with Hyfe. Data will be transferred in encrypted form over a secure line (HTTPS); only the PI or authorized delegate on the research team will have the decryption key. The software used for handling transfers will be a custom-made web application, hosted on the Google Cloud platform on servers physically located in the United States.

11. STATISTICAL METHODS

The primary feasibility outcomes will consist of recruitment rate, retention rate, adverse events, compliance, and acceptability of the HROM assessment. The recruitment rate, consisting of the eligibility and consent rate will be calculated with 95 % confidence intervals (CI). A table showing baseline demographic and clinical characteristics for each group will be presented to indicate any differences between groups. Participant characteristics will be summarised using appropriate statistics. Medians (IQR) will be reported for ordinal data, mean (standard deviation) for continuous data and raw count (number (%) will be reported for nominal data.

For the clinical outcomes, all HROM data will be recorded, and median metrics will be recorded for the overall participant cohort and will be broken down into smaller categories based on primary respiratory diagnoses. Questionnaire data will be reported for all participants and mean scores will be reported. A table showing baseline demographic and clinical characters will be presented. Participant characteristics will be summarised using appropriate statistics. Medians (IQR) will be reported for ordinal data, mean (standard deviation) for continuous data and raw count (number [%]) will be reported for nominal data.

Comparison of baseline and follow-up HROM and questionnaire data will be made using paired ttests for normally distributed data and Mann-Whitney U testing for skewed data. Averages of all

HROM metrics and questionnaire data will be presented in tables and p-values of the statistical tests will be displayed alongside this data.

Safety data will be summarised using descriptive statistics.

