	2. Data quality: Completion of clinical outcomes at follow-up and patterns of	
	missing data for the trial measures. Completion of participant symptom questionnaires throughout the study. Completion of trial processes, principally HROM.	
	3. Acceptability of assessment: Quantify the proportion of participants who judge the trial investigations, principally HROM, to be acceptable.	
	Exploratory clinical outcomes	
	1. Oesophageal functioning: To evaluate the effect of azithromycin on the contraction vigour and swallow coordination. This will be evaluated by investigating patients with HROM before and 1 month after initiation of azithromycin as part of routine clinical care.	
	2. Symptom burden: Symptoms will be assessed before and 1 month after initiation of azithromycin as part of routine clinical care. Symptoms will be measured using validated symptom questionnaires, visual analogue scale for cough, and numeric rating scales for breathlessness	

	 Relationship between oesophageal motility and symptoms: The change in oesophageal functioning and presence of respiratory symptoms will be examined in each participant. The relationship between these two parameters will then be examined using statistical analysis. Effect of azithromycin therapy on continuous objective cough frequency as measured by the Hyfe Cough Tracker©. Relationship between continuous objective cough frequency data and subjective repetitive cough evaluation as measured by cough VAS.
Trial Design	A prospective pilot trial of a single group of patients with chronic respiratory disease being investigated with HROM and treated with azithromycin as part of routine clinical care.
Number/Type of Participants	Thirty individuals with chronic respiratory disease who are being commenced on azithromycin as part of routine clinical care.
Inclusion Criteria	 Males and females aged ≥18 years. Have a diagnosis of chronic respiratory disease (COPD, asthma, interstitial lung disease, chronic cough, cystic fibrosis, and/or bronchiectasis) confirmed by a consultant respiratory physician. Exhibit symptoms consistent with airway reflux, demonstrated by a score ≥14 on the Hull Airways Reflux Questionnaire Are being initiated on azithromycin treatment as part of routine clinical care by their usual clinician. This will include all common treatment regimes, 250mg once daily, 250mg three times per week, and 500mg three time per week. Are willing and able to consent to all trial procedures.

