Exclusion Criteria	 Previous treatment with long-term macrolides in the past 3 months. Unable to be investigated with HROM due to contraindications such as anatomical abnormalities or diseases of the oesophagus or unwilling/unable to be investigated with HROM based on the clinical judgement of the investigators due to severity of lung disease. Have another cardiorespiratory cause for their symptoms (such as heart failure or lung cancer). Are unable or unwilling to consent to or complete the trial procedures. Women of child bearing potential not using effective means of contraception. Effective methods of contraception include any oral contraceptive pill, any intrauterine device, any long term contraceptive implant, and any long-acting contraceptive injection Have been involved in another medicinal trial (CTIMP) within past four weeks.

Trial Treatment(s)	Trial Participants will be commenced on azithromycin therapy as part of usual clinical care.
Trial Endpoints and Statistical Methods	For trial endpoints, appropriate statistical analysis will be performed to compare HROM metrics and symptom questionnaire data at baseline and at follow-up.
	A table showing baseline demographic and clinical characteristics for each group will be presented. Participant characteristics will be summarised using appropriate statistics. Medians (interquartile range) will be reported for ordinal data, mean (standard deviation) for continuous data and raw count (number, %) will be reported for nominal data.
	For participant outcome data, descriptive statistics, mean (standard deviation) for continuous outcomes and raw count (%) for categorical outcomes, will be reported for each group at baseline and at 1-month follow-up, and for continuous objective and subjective cough data where applicable.
Safety Analyses	AEs/SAEs will be listed and summarized using descriptive statistics.
Sample Size Rationale	As this is a pilot study, a formal sample size calculation has not been performed. We will recruit 30 participants over 12 months based on National Institute for Health Research recommendations for pilot/feasibility studies.

SCHEDULE OF ASSESSMENTS AND PROCEDURES

Visit	Screening Visit	Baseline visit		Follow up visit
Day	-28 to -7	0		28 to 42
Procedure/Assessment			mi i	
Written Informed Consent	Х			
Inclusion/ Exclusion Criteria	Χ	Х		
Invitation Experience survey	Χ			
Setup of the Hyfe Cough Tracker©	Χ			
Monitoring of cough frequency using the Hyfe Cough Tracker©	X**	Х		Х

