3. TRIAL DESIGN

A prospective observational trial evaluating the effect of 1 month (up to 6 weeks) of azithromycin treatment on oesophageal motility and symptom burden in patients with chronic respiratory disease who are being commenced on azithromycin as part of routine clinical care. Participants will be investigated using HROM before and during treatment with azithromycin to evaluate the change in oesophageal function.

The trial team will not be prescribing the azithromycin treatment for the participants, as this will be the decision and the responsibility of their usual treating clinician. However, it is anticipated that all participants will be treated with azithromycin 250 milligrams once daily or three times per week throughout the duration of the study. The acceptability of HROM as a diagnostic tool will be assessed through participant experience surveys. We will also analyse other feasibility outcomes such as eligibility to recruitment ratio and participant retention rate to ascertain how willing participants will be to engage in all trial procedures to inform larger clinical trials/ mechanistic studies.

Participants will be investigated with validated questionnaires to ascertain their symptom burden before and during treatment with azithromycin. With this information we will correlate changes in oesophageal function and symptom burden in this group of patients. Participants will also be asked to use the Hyfe Cough Tracker© equipment (to be further determined - if a dedicated smartphone running the application or a wearable smartwatch running the application) for at least one week prior to their initiation of azithromycin and for the duration of their azithromycin treatment whilst in the trial. We will then observe the difference between daily cough counts before and after azithromycin treatment and be able to ascertain how this correlates with oesophageal function. Additionally, we will look into the relationship of objective cough frequency data and repetitive subjective cough evaluation using cough VAS.

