6.2 HROM Testing Measures

The following HROM test variables will be assessed:

- Distal Contractile Integral: The average DCI from the 10 liquid swallows will be collected and will be used to quantify the vigour of oesophageal contraction.
- Integrated Relaxation Pressure: The average IRP4sec is defined as the average minimum oesophagogastric junction pressure for 4 seconds of relaxation and will be ascertained by the collecting the average measurement over the 10 liquid swallows. This will give a quantification of the adequacy of relaxation at the oesophagogastric junction.
- Lower Oesophageal Sphincter Resting Pressure: Basal and relaxation LOS pressure measurements will be taken, and the LOS Resting Pressure will be measured for all participants.
- Chicago Classification: Using Version 4.0 of the Chicago Classification we will provide each
 participant with a manometric diagnosis. These diagnoses include: Normal Motility,
 Ineffective Oesophageal Motility, Absent Contractility, Achalasia, EGJ Outflow Obstruction,
 Hypercontractile Oesophagus, and Distal Oesophageal Spasm. Participants will receive a
 classification at baseline and at follow-up.
- Presence of a Hiatus Hernia: All HROM examinations will be analysed for likelihood of the presence of a hiatus hernia.

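### Skewed baseline and follow-up data from the same patients are to be compared with Mann-Whitney U, an independent-samples test, where a paired rank test is needed

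*Protocol*

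**What the plan says.** The Synopsis (Trial Design) describes "A prospective pilot trial of a single group of patients with chronic respiratory disease". Section 3 sets out the repeated measurement. For manometry: "Participants will be investigated using HROM before and during treatment with azithromycin to evaluate the change in oesophageal function". For symptoms: "Participants will be investigated with validated questionnaires to ascertain their symptom burden before and during treatment with azithromycin". Follow-up is at day 28 to 42 (Section 7.5), and the recruitment target is 30 (Synopsis, Sample Size Rationale).

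The tests are fixed in Section 11: "Comparison of baseline and follow-up HROM and questionnaire data will be made using paired" t-tests when the data are normal and Mann-Whitney U when they are skewed. The full pair of choices reads "paired ttests for normally distributed data and Mann-Whitney U testing for skewed data". The results tables will carry the outcome of these tests: "p-values of the statistical tests will be displayed alongside this data". No section names a paired rank test.

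**The concern.** The sentence recognises the pairing in its first branch and drops it in the second. With normal data each participant serves as their own control. With skewed data the same measurements would be handled as two unrelated samples, up to 30 baseline values and 30 follow-up values, as if they came from 60 people.

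The second branch is likely to be used often. Section 11 itself plans medians for the HROM metrics, which suggests that skewness is expected there, and several questionnaire scores are ordinal. The contractile integral and the sphincter pressures in Section 6.2 carry the question in the trial's title, whether azithromycin changes oesophageal motility. A test that cannot use the pairing could report no change where there is one. Section 3 says the study is meant to inform larger trials and mechanistic studies, so a missed signal has consequences. Whether a given variable is analysed as paired or unpaired would also depend on how its distribution happens to look.

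Two smaller faults lie in the same sentence. The paired t-test requires approximate normality of the within-participant differences, but the sentence speaks only of normally distributed data. Also, the HROM variables in Section 6.2 include Chicago Classification at both visits and hiatus hernia. Neither is numeric, so neither named test suits them.

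**Working it through.** **Inputs from the Protocol.** One group; two visits per participant; target of 30 participants; paired t-test or Mann-Whitney U according to shape. The Protocol gives no power, alpha, effect size, SD or within-patient correlation for these comparisons, so there is no stated figure to reproduce.

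**Assumptions (not in the Protocol).** Two-sided alpha 0.05; log-normal data with log SD 1; within-patient correlation 0 to 0.8 on the log scale; true shift of 0 (type I error) or 0.5 SD on the log scale (power); 30 pairs, and 24 pairs to allow for loss. The allowance is needed because participants who stop azithromycin do not repeat HROM (Section 4.4) and treatment deviations are excluded from analysis (Section 5.2). Thirty pairs is therefore the maximum.

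**Step 1: why the pairing matters.** With SD 1 at each visit and correlation ρ, the paired change has variance 2(1 − ρ). An independent-samples test works as if it were 2. The standardised paired change for a 0.5 shift is 0.5/√(2(1 − ρ)):

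- ρ = 0.3: 0.5/√1.4 = 0.42
- ρ = 0.5: 0.5/√1.0 = 0.50
- ρ = 0.7: 0.5/√0.6 = 0.65
- ρ = 0.8: 0.5/√0.4 = 0.79

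A paired test gains as this rises. Mann-Whitney does not.

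**Step 2: approximate true type I error of Mann-Whitney.** Under pairing, its z statistic has null variance of about 1 − ρs, where ρs = (6/π)·arcsin(ρ/2) is the Spearman correlation. The actual alpha is then about 2[1 − Φ(1.96/√(1 − ρs))].

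- ρ = 0.3: ρs = 0.288, alpha ≈ 0.020
- ρ = 0.5: ρs = 0.483, alpha ≈ 0.006
- ρ = 0.7: ρs = 0.683, alpha ≈ 0.0005
- ρ = 0.8: ρs = 0.786, alpha < 0.0001

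**Step 3: simulation, 10,000 replicates per cell, 30 pairs.** The signed-rank test is applied to the raw differences.

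| Correlation | Type I error, Mann-Whitney | Type I error, signed-rank | Power, Mann-Whitney | Power, signed-rank |
|---|---|---|---|---|
| 0 | 0.047 | 0.048 | 0.46 | 0.42 |
| 0.3 | 0.021 | 0.050 | 0.44 | 0.54 |
| 0.5 | 0.006 | 0.045 | 0.44 | 0.67 |
| 0.7 | 0.002 | 0.048 | 0.44 | 0.86 |
| 0.8 | 0.0001 | 0.051 | 0.43 | 0.95 |

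The simulated type I error agrees with Step 2 at correlations 0.3 and 0.5. At 0.7 it is somewhat larger (0.0016 against 0.0005), but both are far below the nominal level.

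**Step 4: fewer pairs.** With 24 pairs, power is 0.35 against 0.44 at correlation 0.3, 0.33 against 0.56 at 0.5, 0.31 against 0.77 at 0.7, and 0.29 against 0.90 at 0.8 (Mann-Whitney first).

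**Step 5: sensitivity to the spread.** With log SD 0.8 and 30 pairs, power is 44% against 67% at correlation 0.5, 43% against 87% at 0.7, and 44% against 97% at 0.8. The pattern does not depend on the log SD chosen.

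**The case against.** The strongest defence concerns importance. Section 6.1 makes feasibility and acceptability the primary outcomes, and oesophageal function and symptoms are labelled exploratory. No sample size, alpha or progression rule depends on these p-values. With positive correlation the error does not create false positives. At a low correlation such as 0.3 the loss is modest, 44% power against 54%, and at zero correlation Mann-Whitney is slightly the better of the two (46% against 42%). All of this stands. It limits the consequences but does not make the test suitable.

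It could also be said that Mann-Whitney is meant for comparisons between diagnostic subgroups. The wording rules this out, because the subject of the sentence is baseline against follow-up. Nor is this a detail left to a statistical analysis plan: the Protocol names a specific test, and that test does not match the design.

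On the secondary points the defence is stronger. The Protocol does not say which quantity is checked for normality, and a later plan could settle it. The Synopsis already promises counts and percentages for categorical outcomes at both visits, and a purely descriptive treatment of Chicago class and hiatus hernia is acceptable in a pilot of this size. A formal test for them, or a particular estimator of the paired change, is an optional improvement.

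**Conclusion.** The concern holds. Section 11 prescribes an independent-samples test for a within-patient comparison, so p-values from that branch are invalid whenever the two visits are correlated. That conclusion follows from the design alone and needs no assumption about effect size.

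The size of the loss does depend on assumptions. For correlations of 0.3 to 0.8 under the settings above, the power given up is about 9 percentage points at 0.3 (53.6 − 44.2), 22 at 0.5 (66.7 − 44.3), 42 at 0.7 (86.4 − 44.2) and 52 at 0.8 (95.4 − 43.4). The error runs towards missing real change. It affects the exploratory motility and symptom results, and leaves the feasibility, acceptability and safety reporting unaffected. It should still be corrected before analysis, because the p-values will be tabulated and the correction is trivial.

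**What to change.** In Section 11, replace Mann-Whitney U testing with the Wilcoxon signed-rank test on within-participant differences (follow-up minus baseline), and state that normality is judged on those differences.

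Two additions are worth making in the same edit but are not essential. First, report the paired change with a 95% confidence interval beside each p-value: the mean change for the t-test, or the Hodges-Lehmann estimate for the signed-rank test. Second, state that Chicago Classification and hiatus hernia fall outside these two tests and are described by counts at each visit. If a test is wanted for hiatus hernia, or for motility reduced to normal against abnormal, an exact McNemar comparison fits the pairing.

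The cost is one sentence for the essential change. It requires no new data, visits or participants.
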